Protocol

Randomized Clinical Trial of Intraoperative ECMO versus Cardiopulmonary Bypass in Lung Transplantation

Amendment 1. September 27, 2017

TABLE OF CONTENTS

DEFINITIONS, ACRONYMS, AND ABBREVIATIONS.

ABSTRACT.

BACKGROUND AND SIGNIFICANCE

ENDPOINTS.

STUDY DESIGN.

STUDY POPULATION.

DEFINITIONS AND MEASUREMENT OF ENDPOINTS.

CLINICAL CENTERS.

DATA COLLECTION.

DATA MANAGEMENT

ANALYTIC PLAN.

REFERENCES.

DEFINITIONS, ACRONYMS, AND ABBREVIATIONS

CPB Cardiopulmonary bypass

ECMO Extracorporeal membrane oxygenation

PGD Primary Graft Dysfunction

STUDY INVESTIGATOR

PI: [name]

Co-Authors

[name]

[name]

[name]

[name]

[name]

[name]

[name]

[name]

ABSTRACT

Title	Randomized Clinical Trial of Intraoperative ECMO vs. Cardiopulmonary Bypass in Lung Transplantation
Background	Cardiopulmonary bypass (CPB) is the current standard of care for intraoperative cardiorespiratory support during lung transplantation. However, the blood-air interface and the need for full systemic anticoagulation may lead to systemic inflammatory response and coagulopathy. Some reports have suggested that intraoperative support with extracorporeal membrane oxygenation (ECMO) in lieu of CPB may be a better alternative with decreased bleeding, blood requirements and rates of primary graft dysfunction (PGD).
Hypothesis	patients on ECMO will have 
• decreased transfusion requirements,• decreased intubation time,• lesser PGD grade at 72 hours• No increase in major adverse events• Pump duration may be longer.
Study Design	A prospective randomized trial comparing intraoperative support with ECMO and CPB. This will be a superiority trial for efficacy and non-inferiority for safety. The allocation ratio will be 1:1.
Number of Participants	40 in each arm
Study Objectives	Determine if ECMO compared to CPB during lung transplantation has a beneficial effect on

	short term outcomes after lung transplantation.
Interventions	When patient need intraoperative cardiopulmonary support, patient would be randomized to ECMO or CPB
Inclusion Criteria	All patients undergoing lung transplantation. Not all patients randomized will need intraoperative support
Exclusion Criteria	
Patients undergoing concomitant cardiac operations with indication for obligate use of cardiopulmonary bypass
 
Patient with specific anatomy that require full cardiac decompression such as severe pulmonary hypertension or large heart that are shifted severely into the left chest (relative)
 
Patients with high likelihood of significant pleural bleeding that will require returning the blood back into the cardiotomy reservoir (relative)
 
Patients bridged to transplant with ECMO
 
Patients who the surgeon feels would be better served with CPB rather than ECMO These patients will be entered into a registry and followed.

1 ° Endpoint	1 Bleeding: total PRBC transfusion requirements at 72hours
2 ° Endpoint	
Superiority
 
 1. Ventilation time (days) 2. Intraoperative PRBC transfusion rates 3. Duration of support 4. Primary graft dysfunction (PGD) grade at 72 hours. 5. Transfusion requirement of FFP, platelets, cryoprecipitate at 72 hours. 
Non-inferiority:
 
 6. Composite outcome of: 30-day or discharge date (if earlier than 30 days) mortality, bleeding requiring

	reoperation, new ECMO, new renal failure requiring dialysis
Baseline and Clinical Outcomes Data	From: EDIT database, EPIC Medical records review

BACKGROUND AND SIGNIFICANCE

The Problem

In lung transplantation where cardiopulmonary support is needed intraoperatively, the usage of CPB is historically and still currently the standard of care at most centers worldwide.

While cardiopulmonary bypass allows for versatility and the conditions necessary to complete many transplant operations, there are disadvantages, such as the need for full dose heparinization with the associated risk of bleeding, and the activation of inflammatory mediators which have the potential to lead to higher degrees of postoperative primary graft dysfunction (PGD). To counter some of these complications, ECMO in a veno-arterial (VA ECMO) configuration has been proposed and studied as an alternative method of cardiopulmonary support. Prior reports have suggested that intraoperative support with extracorporeal membrane oxygenation (ECMO) in lieu of CPB may be a better alternative with decreased bleeding, blood requirements and rates of primary graft dysfunction (PGD).

Currently, many centers would use one technique or the other and both are considered current standard of care and best practice. At Cleveland Clinic, we have used both methods. The method of support is currently not discussed with patients as both are considered acceptable.

HYPOTHESIS

Our hypothesis is that patients on ECMO will have a decreased transfusion requirements, decreased intubation time, lesser PGD grade at 72 hours without increase in adverse risk. Pump duration may be longer.

ENDPOINTS

Primary

- 1 Bleeding: total PRBC transfusion requirements at 72hours

Secondary

Superiority

1. Ventilation time (days)
2. Intraoperative PRBC transfusion rates
3. Duration of support
4. Primary graft dysfunction (PGD) grade at 72 hours.
5. Transfusion requirement of FFP, platelets, cryoprecipitate at 72 hours.

Non-inferiority:

1. Composite outcome of: 30-day or discharge date (if earlier than 30 days) mortality, bleeding requiring reoperation, new ECMO, new renal failure requiring dialysis

STUDY DESIGN

Randomized clinical trial with an allocation ratio of 1:1, comparing CBP versus ECMO for intraoperative cardiopulmonary support. Study will have a superiority design for efficacy and a non-inferiority design for safety.

Randomization:

All lung transplant patients will be consented preoperatively. Patients will be randomized at the beginning of the case and the configuration of the cardiopulmonary bypass machine will be set accordingly. Not all patients randomized will require intraoperative cardiopulmonary support.

Circuit design:

separate tubing that connects the venous return line directly to the pump head bypassing the venous reservoir. The venous reservoir is still connected and but clamped.

Incision and cannulation:

The type of incision will be at the discretion of the surgeon but can be sternotomy, thoracotomy or clamshell. If patient has a sternotomy and randomized to ECMO, venous cannula should be placed through a percutaneous femoral venous cannula to avoid the potential of air embolus.

Anticoagulation:

ACT target 200-250. Repeat every 30 min. Bolus 5000U, give supplemental doses as needed.

Conversion to full cardiopulmonary bypass:

Give full dose heparin; release the clamp on the venous reservoir after act is above 480.

Reasons to convert from ECMO to CPB intraoperatively:

- Significant bleeding to allow blood to return back to circuit

- Heart remain too distended to allow mobilization

- Air in the circuit

- The need to fibrillate or arrest the heart

- Hemodynamic instability from positioning

Other safety mechanisms:

- Consider system for rapid transfusion

- Double lumen intubation: the heart does not decompress and there's ejection requiring the need for ventilation.

- Use an urchin or heartnet for heart positioning if necessary

- Once the patient is decannulated, the blood from the circuit can be re-transfused back into the patient

Transfusion triggers:

Transfusion triggers will be hematocrit of .24 and at the discretion of the staff surgeon, anesthesiologist or intensivist. Coagulopathy will be corrected based on Cleveland clinic post cardiectomy bypass protocol (appendix 2) and at the discretion of surgeon, anesthesiologist or intensivist.

Patients will be extubated at the discretion of the staff surgeon and intensivist.

Patients who are consented but not included in the study and patients who are felt to be better candidates for cpb will be followed in a separate registry

NUMBER OF PARTICIPANTS

40 Patients in each arm

Power calculation (based on 2015 CCF outcomes)

- Safety

 - 30 day mortality: 6.2%

Bleeding requiring reoperation: 10.3%
New ECMO: 1.3%
New renal failure requiring dialysis: 10.3%
Composite outcome 18.6%.

Sample size calculation
Non-inferior margin: 5%
90%: 283, 80%:205, 70%: 155
Non-inferior margin: 10%
90%: 77, 80%:56, 70%: 42

Efficacy

PGD grade at 72 h:

0:	24.4%
1:	47.4%
2:	14.1%
3:	14.1%

RBC transfusion

CPB: 14.7(8.4) vs ECMO 9.3(6.9)
90%: 51, 80%:39, 70%: 30

Ventilation time

CPB: 16.5days (27.3) vs ECMO 8.25 (16.4)
90%: 83, 80%:62, 70%: 49

For literature outcomes, see appendix 1.

STUDY POPULATION

The study population will be all patients undergoing lung transplantation at our institution. These patients will be randomized using the block method and allocated to either the CPB or ECMO group. Not all patients randomized will require intraoperative support.

Inclusion Criteria

All consented patients undergoing lung transplantation.

Exclusion Criteria

Patients undergoing concomitant cardiac operations with indication for obligate use of cardiopulmonary bypass

Patient with specific anatomy that require full cardiac decompression such as severe pulmonary hypertension or large heart that are shifted severely into the left chest (relative)

Patients with high likelihood of significant pleural bleeding that will require returning the blood back into the cardiotomy reservoir (relative)

Patients bridged to transplant with ECMO

Cystic fibrosis/bronchiectasis/resistant infection patients where surgeon will need to remove both lungs prior to implantation

Patients who the surgeon feels would be better served with CPB rather than ECMO
These patients will be entered into a registry and followed.

CLINICAL CENTERS

Patient Confidentiality

All patient records will be kept confidential according to HIPAA guidelines. Study investigators and site Institutional Review Boards (IRBs) may review source documentation as necessary, but will then transmit this information to Clinical Investigations at Cleveland Clinic according to the patient's unique study number. Linkage of that study number to the actual patient will reside only at the individual institutions. Aggregate data from this study may be published as per publication policy documented in the trial agreements; no data with patient identifiers will be published.

Consent

Patients will be consented for surgery ahead of time at time of listing

DATA COLLECTION

Data will be collected from Epic Systems chart review and supplemental data collection. All necessary data are currently already collected. Study terminates at patient discharge. No additional testing or followup is needed beyond what is already done for this patient population.

DATA MANAGEMENT

The data will be stored in Red Cap Sheets strictly secured and managed by the lead and other co-investigators. No identifiable information will be shared with outside parties, ensuring that all data will remain safely stored on Cleveland Clinic Main Campus user hard drives and will only be shared amongst our study team.

ANALYTIC PLAN

Basic statistical analysis will be required to compare the outcomes in the groups. Patients who are excluded will be included in a separate registry.

Analysis will be based on intention to treat.

A statistical significant difference is defined as a two-sided P value less than 0.05.

REFERENCES

1. Machuca (2015) Outcomes of intraoperative extracorporeal membrane oxygenation versus cardiopulmonary bypass for lung transplantation.
2. Bermudez (2014) Outcomes of Intraoperative Venoarterial Extracorporeal Membrane Oxygenation Versus Cardiopulmonary Bypass During Lung Transplantation.
3. Ius (2012) Lung transplantation on cardiopulmonary support: Venoarterial extracorporeal membrane oxygenation outperformed cardiopulmonary bypass.
4. Hoechter (2015) The Munich Lung Transplant Group: Intraoperative Extracorporeal Circulation in Lung Transplantation.

Appendix 1

Outcomes from Literature on CPB vs. CPB

	CPB	ECMO
Surgical time (min)	444	425
Heparin intraop (IU/kg)	490.1	54.6
ECC time (min)	203.5	216
Crystalloid (mL)	2484	3466
Colloid (mL)	1500	1300
Cell saver (mL)	690	500
Intraop Transfusion (units)	PRC 9 units FFP 8.5 units Platelets 3.5 units FibGen 5 (g) PPSB 3 (IU) TXA 2.5 (mg)	PRC 6 FFP 9 Platelets 2 FibGen 0 (g) PPSB (prothrombin complex concentrate) 0 (IU) TXA 2 (mg)
Overall Transfusion (units)	PRC 16 FFP 13 Plts 4 FibGen 4 PPSB 2.5 (IU) TXA 2.5 (mg)	PRC 8 FFP 15 Plts 2 FibGen 0 PPSB 0 (IU) TXA 2 (mg)
ECMO prolonged into postop (n)	6	15
→Duration of prolonged ECMO (days)	4	3
→Graft failure/reperfusion injury (n) (indication for prolonged ECMO)	2	9
→pHT /hemodynamic (n) (indication for prolonged ECMO)	4	6
Redo-surgery (n)	15	13
Ventilator support (days)	21	4.5
ICU LOS (days)	36	14.5
ICU free survival (days)	54	72
Hospital LOS (days)	47	42.5
Hospital free survival (days)	14	36.5
30 day mortality (n)	1	3
One year mortality (n)	4	5

Hoechter (2015): ECMO perioperative advantages (CPB higher transfusion, ventilator support, ICU stay), long-term not affected (same 30 day and 1 year mortality); excluded bridge to ECMO; * 2 analyses (1) CPB and ECMO (2) full-dose and low-dose heparinization during ECC; (better outcomes in ECMO related to heparin use not the ECC device; yet independent of heparin the ECMO still better at reducing PGD/hemodynamic instability (retrospective, N=188)

	CPB	ECMO
--	------------	-------------

Intraop ischemic time (min)	363	375
ECC support (min) mean	232.5	366.6
Intraop transfusion (units)	RBC 5.9 FFP 3.1 Platelets 8	RBC 7.7 FFP 3 Platelets 4
Periop transfusion (72 hrs) (units)	RBC 14.9 FFP 9.3 Platelets 11	RBC 13 FFP 8.4 Platelets 10.7
Postop initial ventilation (hrs)	226	184.7
Reintubation (n)	80 (36%)	10 (20%)
Postop total ventilation (hrs)	380	250
ICU LOS	21.9	15
Hospital LOS (days)	43	41
Reoperation for bleeding (n)	39 (17%)	4 (8.2%)
Postop renal failure requiring dialysis (n)	49 (22%)	4 (8%)
Postop ECMO (severe PGD) (n)	34 (15%)	9 (18%)
30 day mortality (n)	11 (5%)	2 (4%)
1 year mortality (n)	42 (19%)	9 (19%)

Bermudez (2014): ECMO decreased pulmonary (reintubation)/renal complications, (same severe PGD, perioperative rbc transfusion, mortality long term 30d 6m), longer time on support / more RBC intraop transfusion for ECMO(included cardiac procedures) (CPB n= 222, ECMO n=49)

	CPB	ECMO
Ischemic time (min)	518 L, 432 R, 495 single lung	581 L, 450 R, 400 single lung
ECC time	162 min	Not given
Intraop transfusion (units)	PRBS 12 2.5 platelet concentrate 7.2 FFP 2 fibrinogen	PRBS 7.1 1.5 platelet concentrate 7.1 FFP 1.6 fibrinogen

	4 prothrombin complex concentrate	3.7 prothrombin complex concentrate
Postop transfusion (units)	PRBC 17.9 PC 4.8 17.6 FFP Fibrinogen 0.6 (g) prothrombin complex concentrate 1.3	PRBC 12.7 PC 3.3 11.1 FFP Fibrinogen 0.5 (g) prothrombin complex concentrate 2.7
New postop ECMO support	26%	4%
Postop VA ECMO (n)	1 (2%)	19 (41%)
Rethoracotomy for bleeding (n)	16 (35%)	9 (19)
New requirement for dialysis (n)	22 (48%)	6 (13%)
Ventilation time (days)	21.4	14
ICU LOS (days)	29	19
In-hospital mortality	39%	13%
Survivors at discharge (n)	28 (61%)	40 (87%)
Survival rate at 3 months (%)	70%	87%
Survival rate at 12 months (%)	56%	81%

lus (2012): 2 groups; significant in hospital mortality reduction with ECMO , lower rates of PGD and renal failure. ECMO better periprocedural management, less postop complications; increased survival despite greater preoperative morbidity, transfusion req, postop complications (hemodialysis) (did not exclude cardiac procedure) (N=46 CPB and ECMO groups)

	CPB	ECMO
Intraop pump time (min)	199	210
Warm ischemic time (min)	69 L, 64 R, 74 single	73 L, 70 R, 74 single
Intraop Transfusion (units)	6 pRBC 1 Platelets 4 FFP	3 pRBC 0 Platelets 0 FFP
Postop Transfusion up to 72 hrs	2 pRBC	1 pRBC
Length of mechanical ventilation (days)	7.5	3
ICU LOS (days)	9.5	5
Hospital LOS (days)	27	19

Extracorporeal life support postop requirement (n)	5	0
Dialysis req (n)	12 (18%)	3 (9%)
Reoperation for bleeding (n)	18 (27%)	3 (9%)
90 day mortality (n)	10 (15%)	2 (6%)

Machuca (2015): ECMO may be considered as first choice cardiorespiratory support during LT

a. Excluded: patients bridged w extracorporeal life support, required emergency cannulation for cardiopulmonary support, concomitant cardiac procedure/transplant, B cenocepacia; b. Matched: age, lung transplantation indication, procedure type (bil/single), Recipient factors similar (BMI, gender, donor info) c. Outcomes i. Perioperative: blood product transfusion ii. Early outcomes: mechanical ventilation requirement, ICU stay, hospital stay iii. 90day mortality (33 ECMO matched with 66 CPB)

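### The safety composite stops counting deaths at discharge when that precedes day 30, so its observation window depends on length of stay; any bias would favour ECMO, but its size is unknown and probably small

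*Combined protocol and SAP*

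**What the plan says.** The Abstract and the Endpoints section define the non-inferiority composite in the same words. Its first element is "30-day or discharge date (if earlier than 30 days) mortality", followed by bleeding requiring reoperation, new ECMO, and new renal failure requiring dialysis. No time window is attached to the last three.

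Data Collection states "Study terminates at patient discharge" and continues "No additional testing or followup is needed beyond what is already done for this patient population".

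Number of Participants bases the safety planning on the centre's 2015 outcomes: "30 day mortality: 6.2" percent, and "Composite outcome 18.6" percent. Two margins are listed, "Non-inferior margin: 5" percent and "Non-inferior margin: 10" percent, without a choice between them. Each arm has 40 patients.

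**The concern.** A window that ends at the earlier of day 30 and discharge gives patients different lengths of observation, and its end is a post-randomisation event. The Hypothesis section expects shorter intubation with ECMO, so earlier discharge in that arm is plausible. If it occurs, the ECMO arm has fewer days in which a death can count, and the composite moves towards non-inferiority for a reason unrelated to safety.

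The silence on the other three components leaves two readings. If the mortality phrase governs the whole list, they too are cut at an early discharge. If it does not, they run to discharge, and a patient still in hospital after day 30 can accrue events that a patient who has left cannot. Either way, what is captured depends on length of stay.

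The planning rate is also labelled as 30-day mortality, while the endpoint may stop sooner.

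**Working it through.** **1. The plan's own figures.** The safety sample sizes do not enter this point, but I tried to reproduce them. The formula is n per arm = 2p(1−p)(z₁₋α + z_power)²/margin², with p = 0.186 in both arms, one-sided α = 0.05 and an absolute margin. For power of 90/80/70% it gives:

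| Margin | Formula | Stated |
|---|---|---|
| 5 points | 1038 / 749 / 570 | "90%: 283, 80%:205, 70%: 155" |
| 10 points | 260 / 188 / 143 | 77 / 56 / 42 |

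The stated figures are not reproduced. That is a separate and larger problem, and nothing below rests on it.

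**2. Expected events per arm of 40.** Deaths: 40 × 0.062 = 2.48. Composite events: 40 × 0.186 = 7.44.

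**3. Hospital stay in Appendix 1 (days), capped at 30.**

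| Series | CPB | ECMO | Capped CPB | Capped ECMO |
|---|---|---|---|---|
| Retrospective, N = 188 | 47 | 42.5 | 30 | 30 |
| 222 CPB, 49 ECMO | 43 | 41 | 30 | 30 |
| Matched, 66 CPB, 33 ECMO | 27 | 19 | 27 | 19 |

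The fourth series gives no hospital stay. In the matched series, 30 − 27 = 3 days (CPB) and 30 − 19 = 11 days (ECMO) would be unobserved at the reported stay. In the other two there is no difference at the reported values. This is a rough guide only: a capped summary is not the mean of capped stays, and a summary above 30 days does not exclude individual discharges before day 30.

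**4. Deaths missed.** The documents do not give the share f of 30-day deaths that follow discharge, so I assume a range. I place the whole loss in the ECMO arm and suppose that no missed patient had another component. Deaths missed = 2.48f; fall in the arm's composite = 6.2f points.

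| Assumed f | Deaths missed per 40 | Largest fall (points) |
|---|---|---|
| 10% | 0.25 | 0.6 |
| 25% | 0.62 | 1.6 |
| 50% | 1.24 | 3.1 |
| 100% (ceiling) | 2.48 | 6.2 |

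**5. Effect on the test.** The plan gives no non-inferiority alpha. I assume one-sided 0.025 (half of the two-sided 0.05 in the Analytic Plan), an absolute margin M, and a normal approximation. Suppose the true ECMO excess equals M and the observed ECMO rate is lowered by b. Then type I error = Φ(b/SE − 1.96), with SE = √{[0.186 × 0.814 + p(1−p)]/40} and p = 0.186 + M − b.

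Example, M = 0.10 and b = 0.0155: p = 0.2705, SE = 0.0934, b/SE = 0.166, type I error = Φ(−1.794) = 0.036.

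For f = 10/25/50%, the results are 0.029/0.036/0.052 at the 10-point margin and 0.029/0.037/0.054 at the 5-point margin. Each is an upper bound for its assumed f.

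**6. Overlap between components.** The four component rates sum to 6.2 + 10.3 + 1.3 + 10.3 = 28.1%, against a composite of 18.6%, so some patients have more than one. The three non-fatal components alone sum to 21.9%, which exceeds 18.6%. The planning figures therefore allow deaths to add anything from 0 to 6.2 points of their own. A missed death changes the composite only when it was that patient's sole event.

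**The case against.** The best defence is that the endpoint is secondary, worded identically in both places and consistent with the end of study at discharge, so nothing contradicts itself. Few deaths are expected, components overlap, and in two of the three series the reported stays exceed 30 days. Even in the third, both arms lose time, so the net effect is smaller than a loss in one arm. All of this stands, and it limits the size. It does not remove the fault: deaths between early discharge and day 30 go uncounted. Nor is equal loss harmless. If both arms lose the same share f, a true difference in deaths is observed as (1 − f) times its value, which favours a non-inferiority finding when ECMO is worse.

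Four stronger readings are tempting, and the documents do not support them:

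- *The windows will differ by arm as 27 does from 19 days.* That takes one series of three and ignores that this centre's stays are not given.
- *A whole event is lost.* One event is 1/40 = 2.5 points, half of a 5-point margin or a quarter of a 10-point one. But an expected loss of one death needs 1/2.48 = 40% of 30-day deaths to follow discharge in one arm, with none missed in the other. Nothing in the documents suggests that.
- *The non-fatal components have no end point at all.* The end of study at discharge bounds them; what is missing is an explicit window.
- *The 6.2% is a different quantity from the endpoint.* The labels differ, but the plan does not say whether the 2015 figure captured deaths after discharge.

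**Conclusion.** The point holds in limited form. By its stated rule, the composite misses deaths between an early discharge and day 30, and observation time depends on length of stay. Since all three reported comparisons show shorter stays with ECMO, any differential loss would favour ECMO and non-inferiority.

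The size is unknown and probably small: at most 0.6 to 3.1 points on the ECMO composite for assumed one-arm losses of 10 to 50% of deaths, and less where a patient had another component. This rests on the 6.2% planning rate, 40 per arm and an assumed share of deaths after discharge. How often patients at this centre leave before day 30, and whether that differs by arm, cannot be judged from the documents. I class this as a cheap improvement, not as a threat to the trial.

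**What to change.** - In the Abstract and Endpoints, define the composite as the first of death from any cause, reoperation for bleeding, new ECMO or new dialysis between day 0 and day 30, whether or not the patient has been discharged.
- In Data Collection, change the end-of-study sentence so that outcome ascertainment continues to day 30 for patients discharged earlier.
- Read day-30 status from Epic or routine post-transplant follow-up, and state how vital status is confirmed when there is no day-30 entry. A chart with no entry should not be taken as evidence of survival.
- State whether the 2015 rates of 6.2% and 18.6% were counted over the same window.

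The cost is a minor amendment and a chart look-up for patients discharged before day 30; no new visits are needed. One thing is given up: component events after day 30 in long-stay patients would no longer count.

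### The safety composite counts new ECMO with no rule for ECMO continued from surgery, so the same end-of-case need can be an event after CPB but not after ECMO

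*Combined protocol and SAP*

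**What the plan says.** The ENDPOINTS section and the ABSTRACT list a single non-inferiority endpoint: death, "bleeding requiring reoperation, new ECMO, new renal failure requiring dialysis". STUDY DESIGN assigns safety to the non-inferiority comparison, so this composite carries the formal safety claim.

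The exclusion criteria remove "Patients bridged to transplant with ECMO", so no enrolled patient should arrive on ECMO as a bridge. For intraoperative support, "the configuration of the cardiopulmonary bypass machine will be set accordingly". In the circuit described, "The venous reservoir is still connected and but clamped". STUDY DESIGN lists "Reasons to convert from ECMO to CPB intraoperatively", and the ANALYTIC PLAN states "Analysis will be based on intention to treat".

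The text available does not define *new*, give a time from which ECMO counts, or classify support that continues after surgery. The table of contents names a section on endpoint definitions and measurement, but the body available has no section under that heading.

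Deaths are counted to day 30, or to discharge if that is earlier. It is unclear whether this window also governs the other three components. DATA COLLECTION ends the study at discharge.

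**The concern.** Because bridged patients are excluded, *new* becomes ambiguous only through the randomized treatment. Two patients with the same failing graft at the end of surgery can be coded differently. The one coming off CPB has ECMO started, which is an event. The one already on ECMO stays on it, which on the literal wording is not.

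A safety endpoint ascertained differently by arm weakens a non-inferiority comparison, because events missed only in the experimental arm make the claim easier to reach. With 40 per arm, one patient is 1/40 = 2.5 percentage points.

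**Working it through.** **Inputs from the plan (NUMBER OF PARTICIPANTS).** 40 per arm; composite 18.6%; new ECMO 1.3%; 30-day mortality 6.2%; margins of 5 and 10 points listed, neither named as the choice. The ANALYTIC PLAN gives only a two-sided 0.05 level, which corresponds to one-sided 0.025. No separate non-inferiority level is stated, so one-sided 0.05 is shown as well.

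**The plan's own figure.** For a 10-point margin and 80% power the plan lists 56. The usual formula with 18.6% in both arms, n = (z₁₋α + z₁₋β)² × 2p(1−p)/margin², gives:
- one-sided 0.05: 6.18 × 0.303/0.01, about 188 per arm;
- one-sided 0.025: 7.85 × 0.303/0.01, about 238 per arm.

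The listed figure does not reproduce. That is a separate matter and nothing below depends on it.

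**Literal reading, case by case.**
- CPB during surgery, ECMO started at the end for graft failure: event.
- ECMO during surgery, continued for graft failure: not an event on the plain word *new*.
- ECMO during surgery, removed, restarted later: event.
- ECMO converted to CPB, ECMO afterwards: no rule. Intention to treat fixes the arm, not whether an event occurred.

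The first two cases differ only in the support received during surgery.

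**Illustration of size.** Let X be CPB-arm events, binomial(40, 0.186). Let Y be counted ECMO-arm events, binomial(40, 0.286 − h). The true ECMO rate sits at the assumed 10-point margin (0.186 + 0.100 = 0.286), and h is the share of true events left uncounted. Non-inferiority is declared if

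(Y − X)/40 + z × √[p₁(1−p₁)/40 + p₂(1−p₂)/40] < 0.10,

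where p₁ = X/40 and p₂ = Y/40. Probabilities are summed exactly over all outcomes.

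| Uncounted, h | One-sided 0.025 | One-sided 0.05 |
|---|---|---|
| 0 | 2.8% | 5.3% |
| 1.3 points | 3.8% | 7.0% |
| 3 points | 5.7% | 9.9% |
| 5 points | 8.7% | 14.3% |

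The 1.3-point row borrows the site's new-ECMO rate as a scale. That rate neither estimates nor caps continued support. The row also assumes that none of these patients has another composite event. The listed components sum to 6.2 + 10.3 + 1.3 + 10.3 = 28.1 against a composite of 18.6, so events do overlap, but the documents do not say how much of the overlap falls on ECMO. The 3- and 5-point rows have no basis in site data.

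**One patient at the cutoff.** With 7 CPB events (17.5%), the upper limits are:
- 4 ECMO-arm events, one-sided 0.025: −0.075 + 1.96 × 0.0765 = 0.075, passes;
- 5 events, one-sided 0.025: −0.050 + 1.96 × 0.0796 = 0.106, fails;
- 5 events, one-sided 0.05: −0.050 + 1.645 × 0.0796 = 0.081, passes;
- 6 events, one-sided 0.05: −0.025 + 1.645 × 0.0824 = 0.111, fails.

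The cutoff is therefore 4 events at 0.025 and 5 at 0.05. At either level, recoding one patient just above it changes the conclusion.

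**Mortality window.** The endpoint stops at an early discharge, whereas the planning rate is labelled 30-day mortality; how that rate was counted is not shown. If 5% to 30% of the 6.2% died after discharge (an assumption), the loss is 0.31 to 1.86 points, or 0.1 to 0.7 patients per 40. Hospital stays in Appendix 1 exceed 30 days in both groups in two of the three series that report them (47 vs 42.5 and 43 vs 41 days, CPB vs ECMO) but not in the third (27 vs 19).

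**The case against.** The strongest reply is that the mechanism is not shown at this centre. The intraoperative circuit is a reconfigured bypass machine, and the only text on coming off it describes decannulation: "Once the patient is decannulated, the blood from the circuit can be re-transfused back into the patient". If postoperative ECMO needs a separate circuit, it could be called new in either arm. Moreover, "Not all patients randomized will require intraoperative cardiopulmonary support", which dilutes any difference. All of this stands and limits the point to an ambiguity of unknown size.

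The component also looks rare. At 1.3%, 0.5 patients per 40 are expected (0.013 × 40), and the chance of any is 1 − 0.987⁴⁰ = 41%. This is a secondary endpoint with little power even under perfect coding: with equal true rates and the 10-point margin, non-inferiority is shown 22% of the time at one-sided 0.025 and 32% at 0.05. The unchosen margin and the low power matter more. That lowers the priority but does not remove the asymmetry. The 1.3% is not split by type of support and does not say how continued runs were classified.

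A reader might infer more from Appendix 1. In the series with 46 patients per group, new postoperative ECMO is 26% after CPB and 4% after ECMO, while postoperative VA ECMO is 2% and 41%. This looks like a change of sign depending on how *new* is read. It cannot be used that way. Within the CPB column, all postoperative ECMO could not be rarer than new postoperative ECMO, so the second row must count something else, and neither row is defined.

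A reader might also infer that the wording could equally work against ECMO, if every continued run were counted. The plain word *new* argues against that reading.

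**Conclusion.** The point holds in a limited form. Followed literally, the plan can ascertain its only non-inferiority endpoint differently by arm, and the main direction favours ECMO. The documents support neither a bias of known size nor a finding that support is in fact continued here. At a scale tied to the one site figure, the false non-inferiority rate rises by 1.0 point (one-sided 0.025) or 1.7 points (one-sided 0.05). These figures rest on the assumed 10-point margin, the assumed test, a true excess at the margin, and 1.3 points borrowed as a scale. The single-patient result applies only when the counts fall at the cutoff.

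The discharge cut-off on deaths is a separate and probably small defect. The rule is the same in both arms but ties the observation window to length of stay.

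**What to change.** 1. Use one counting rule in both arms: ECMO after leaving the operating room for graft dysfunction or cardiorespiratory failure is an event, whether continued or newly started and whatever support was received during surgery. Record the indication. Report *newly started only* and *any postoperative ECMO* as sensitivity analyses.
2. Count death, reoperation, ECMO and dialysis to day 30 for every randomized patient, regardless of discharge.
3. Recalculate the 18.6% baseline from the 2015 data under this definition.

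The cost is a wording change, one extra data field, and a day-30 record look-up for patients discharged early, which goes beyond the present end of study at discharge. The indication needs some judgement, best made by an assessor unaware of the arm. The planning rate may change. All of this concerns how events are counted, not how patients are managed.
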